#### Investigational Product Treatment:

Nemolizumab (CD14152) will be administered as a subcutaneous injection, with a loading dose of 60 mg on Day 1, followed by injections of 30 mg every 4 weeks for 12 weeks.

Table 2: Dosing Scheme

Group	Dose on Day 1	Dose at Weeks 4, 8 and 12
1	60 mg	30 mg

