### 7.3 Discussion of Study Design

## 7.3.1 Study Design

This study will evaluate the safety and PK in adolescent AD subjects. The rationale for the general study design is detailed in this section, and is based upon the prior Phase 2b design conducted in adult subjects with AD. The rationale for dose/dose regimen are provided in Section 5.5.

Based on the results of the prior Phase 1, 2a, and 2b and simulation from the pop-PK model, the fixed dose of 30 mg (with a loading dose of 60 mg) was chosen to be administered Q4W in this clinical trial. The selected dose provided the best risk/benefits ratio in adults and is expected to provide similar efficacy and safety in adolescent subjects.

Eligible subjects for this clinical trial will be adolescents with moderate-to-severe AD and associated pruritus whose disease is not adequately controlled by topical treatments. The study population is selected based on the current unmet need in the management of AD in pediatric populations, the mode of action of nemolizumab, and the need to understand the PK and safety of nemolizumab in the adolescent population for dose verification before initiating planned Phase 3 studies, which will also enroll adolescent subjects. The inclusion criteria for IGA, BSA and EASI are consistent with the disease severity targeted in the Phase 3 studies, enrolling adolescents and adults: An IGA of 3 or 4 corresponds to moderate or severe AD, respectively; BSA of at least 10% is usually observed in these more severe AD patients; an EASI threshold of 16 is generally recognized to be representative of moderate-to-severe AD, and is consistent with the published analyses correlating IGA and EASI assessments in patients with AD. 33,34 Finally, subjects with associated pruritus are targeted because of prior studies with nemolizumab and its marked effect on pruritus.

The study includes a 16-week treatment period and an 8-week follow-up period for safety (ie, 12 weeks after last study drug administration at Week 12) for subjects who will not rollover to the nemolizumab long-term extension study. A 16-week treatment period is considered adequate to evaluate the safety and efficacy of nemolizumab based on the results of the Phase 2b study (114322). As steady state in adults can be achieved in 4 weeks, a trial duration of 16 weeks in adolescents was deemed sufficient to assess all study outcomes.

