The duration of the follow-up period (ie, 12 weeks after the last study drug administration), corresponds to 5 half-lives of nemolizumab: the drug plasma level is expected to be lower than the Limit of Quantification at the end of the study, and the follow-up period is therefore considered adequate to ensure the safety of subjects.

Background therapy including moisturizer and authorized TCS will be used throughout this study. This is in line with the current practice to use topical agents in conjunction with systemic treatment in more severe cases. Background TCS will be started from the screening visit, to ensure disease stability and avoid flares. The potency of TCS selected for this study is clinically justified. A medium potency TCS will be used on the body where considered safe (eg, trunk and extremities), and a low potency TCS will be used in TCS-sensitive areas (eg, face, neck, intertriginous areas). The prescribed background TCS use should be within daily frequency limits according to the product labeling. Background TCS use includes guidelines to adjust usage to disease activity and

CONFIDENTIAL Page 39 of 99

tolerability of the subject, including tapering when signs and symptoms improve, discontinuation when lesions clear, and restarting if signs and symptoms recur.

Rescue therapy including topical and systemic treatment or phototherapy may be provided if judged to be necessary by the investigator.

This study will assess the PK and safety profile of nemolizumab in the adolescent population, in order to allow their subsequent enrolment in planned Phase 3 studies.

Nemolizumab serum concentration will be assessed at baseline, Weeks 1-2, 4, 8, 12, 16 and Week 24 and at any unscheduled visit for safety reasons. Given that the nemolizumab drug supply configuration and preparation are similar to that used in the Phase 2b study involving adult AD subjects, no change is anticipated in the absorption phase (ka). Thus, limited PK assessment will be done during the absorption phase and serial pre-dose PK samples will be collected at steady state.

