#### 8.2.2 PK Parameters

PK parameters of nemolizumab in the serum will be calculated by the designated CRO using 2 analyses:

PK parameters will be derived using a non-linear mixed effect modeling approach with NONMEM. A pre-specified population PK model based on existing information from previous studies in adults (first-order absorption and a 1-compartment distribution model) will be used to derive empirical Bayes estimates in the adolescent population based on their baseline characteristics, their dosing history and their measured concentrations. The adequacy of the model to properly describe the adolescent data will be based on the model diagnostic tools described in a in a dedicated PK modeling plan. Estimates of main population PK parameters (Cl/F, Vd/F, Tlag, ka), including inter-individual variability, covariate effects, residual error and their relative standard error [RSE]), will be obtained using the popPK model.

- Other individual nemolizumab PK parameters will be derived using the same popPK model (Cmax, Tmax, Ctrough, AUC0-4w, AUC0-8w, AUC0-12w, AUC0-16w, and t1/2).
- In addition, a static analysis based on pre-dose (Ctrough) serum concentration will be
  performed using an NCA. Data from subjects with missing concentration values (missing
  samples) may be used if PK parameters can be estimated using the remaining data points.

For the NCA analysis, the following PK parameters will be determined for each subject based on Ctrough concentration:

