#### 8.3 Immunogenicity

Blood samples will be collected according to Section 7.2 to assess anti-drug (anti-nemolizumab) antibodies (ADA). Serum samples will be assessed for ADA at baseline, Weeks 4, 8, 16, 24 and at any unscheduled visit for safety reasons. ADA will be determined at these time points by the designated CRO using a validated enzyme-linked immunosorbent assay (ELISA) screening assay. The serum concentration will be assessed using a multi-tiered approach.

If serum circulating ADA is detected, presence will be confirmed and characterized (eg, for neutralizing potential) using a validated assay. Incidence of positive ADA results will be summarized (absolute occurrence and percent of subjects).

		Results
will be CSR.		included as an appendix in the final
8.4	Pharmacodynamics	
	and stratum corneum samples will be collected to inve d biomarkers.	estigate the effect of nemolizumab on
Blood s	samples will be collected for assessment of TARC a	and IgE by the central laboratory.

CONFIDENTIAL Page 59 of 99

Protocol Number: RD.06.SPR.116912	Version 6.0

21-JUL-2020

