9.3. Pharmacokinetic Parameters Presentation

Estimates of main population PK parameters (Cl/F, Vd/F, Tlag, ka), including inter-individual variability, covariate effects, residual error and their relative standard error (RSE), will be presented in a dedicated PK report.

Individual derived PK parameters at steady state estimated with the popPK model and individual observed PK parameters at steady state calculated with the NCA will be summarized using the following statistics: n, arithmetic mean, standard deviation, geometric mean, %CV, median, minimum, maximum and 95% CI. This descriptive statistics will be calculated CCI.

In addition, the comparison of the average observed trough (C_{trough}) nemolizumab concentration between ADA+ samples and ADA- samples will be performed using ANOVA and the comparison results will be presented.

All PK parameters will be listed by subject.

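### Steady state at Week 4 and 12 weeks as 5 half-lives do not both hold under the 2:1 load, and the ADA trough ANOVA, with no visit or subject term named, could confound ADA status with visit

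*Protocol*

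**What the plan says.** Protocol 7.3.1 makes three linked statements. To support the 16-week duration: "As steady state in adults can be achieved in 4 weeks". To support the follow-up: the 12 weeks after the last injection "corresponds to 5 half-lives of nemolizumab". On sampling: "serial pre-dose PK samples will be collected at steady state". No numeric half-life appears in the public text.

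The regimen (Protocol synopsis, Investigational Product Treatment) has "with a loading dose of 60 mg on Day 1, followed by injections of 30 mg every 4 weeks for 12 weeks". The population PK model (Protocol 8.2.2) is described as "first-order absorption and a 1-compartment distribution model".

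On antibodies, Protocol 8.3 says: "Serum samples will be assessed for ADA at baseline, Weeks 4, 8, 16, 24" and at unscheduled safety visits. The protocol synopsis leaves the details of the ADA trough comparison to the SAP. SAP 9.3 says "the comparison of the average observed trough (C_{trough}) nemolizumab concentration between ADA+ samples and ADA- samples will be performed using ANOVA". It lists no visits, no visit factor and no subject effect. The title of Table 14.2.3.4 in SAP section 18 describes the same analysis by the subject's antibody status, not by sample.

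**The concern.** Both 7.3.1 statements carry weight. One supports the trial's duration and underlies the description of the pre-dose samples as steady state. The other supports the adequacy of the safety follow-up and the expectation that drug will be unquantifiable at its end. If they imply different half-lives, at least one rationale needs restating.

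The same question reaches the analysis. If troughs fall over the treatment period because the load is wearing off, a comparison of ADA+ with ADA- samples that ignores visit mixes two things. Treatment-related ADA is by definition post-baseline (SAP section 11). If positivity rises over visits, ADA+ samples come disproportionately from visits where every subject's trough is lower. A sample-level ANOVA also treats several samples from one adolescent as independent, whatever the half-life. PK and immunogenicity are both primary endpoints, and this is the only formal ADA-exposure comparison that the SAP names.

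**Working it through.** **Inputs.** From the protocol: 12 weeks (84 days) as 5 half-lives; 60 mg then 30 mg at Weeks 4, 8 and 12; a 28-day interval; one compartment with first-order absorption. Assumed: linear kinetics; ka, which the public text does not give (tested from 0.2 to 1.0 per day and as instantaneous input); and all ADA rates, since the documents give none.

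**1. Checking the 4-week figure against the half-life.**
- Implied half-life = 84/5 = 16.8 days.
- Fraction left after one interval: r = 2^(-28/16.8) = 0.315.
- Troughs in units of one 30 mg dose: W4 = 2r = 0.630; W8 = r(1 + W4) = 0.513; W12 = r(1 + W8) = 0.477; W16 = r(1 + W12) = 0.465.
- Steady-state trough = r/(1 - r) = 0.460.

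| Week | Trough / steady state |
|---|---|
| 4 | 1.37 |
| 8 | 1.12 |
| 12 | 1.04 |
| 16 | 1.01 |

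The fall from Week 4 to Week 16 is 1 - 0.465/0.630 = 26.2%. At ka = 0.2 per day it is 25.9%. If 5 is rounded from 4.5 to 5.5 half-lives, it is 21.7% to 29.8%. Without the load, the Week 4 trough would be 1 - r = 68.5% of steady state. So the 4-week figure is not reproduced with or without the load.

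**2. The reverse check.** Week 4 trough / steady state = 2r/[r/(1 - r)] = 2(1 - r). This equals 1 only if r = 0.5, which is a half-life of 28 days. Then 84/28 = 3 half-lives, and 2^(-3) = 12.5% of the level remains after 12 weeks, against 2^(-5) = 3.1% at 5 half-lives.

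**3. Effect on a pooled ADA comparison, with no true ADA effect.** Within the treatment period, post-baseline trough and ADA samples coincide at Weeks 4, 8 and 16. Take 20 subjects and a 16.8-day half-life. Worked case, ADA+ rates of 0/10/20% (0, 2 and 4 subjects):
- ADA+ mean = (2 × 0.513 + 4 × 0.465)/6 = 0.481.
- ADA- mean = (20 × 0.630 + 18 × 0.513 + 16 × 0.465)/54 = 0.542.
- Difference = 0.481/0.542 - 1 = -11%.

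| Assumed ADA+ pattern at Weeks 4/8/16 | False difference |
|---|---|
| 5/10/15% | -6% |
| 1, 3, 5 of 20 | -8% |
| 0, 4, 4 of 20 | -10% |
| 0/10/20% | -11% |
| 0/0/15%, or 0, 0, 4 of 20 | -14% |
| 4, 4, 4 of 20 | 0% |
| 4, 0, 0 of 20 | +19% |

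Week 24 is 12 weeks after the last injection, so its sample is not a dosing-interval trough. If it were pooled in, 4 subjects positive at Weeks 16 and 24 would give -41%. At a 28-day half-life the Week 4 to 16 troughs do not drift, and this source of confounding disappears.

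**The case against.** A reader might infer that the ANOVA will report the 26% fall as an antibody effect. The documents do not support that. The full 26% would need every ADA+ sample at Week 16 and every ADA- sample at Week 4. The visit confounding depends on the implied half-life, on sample-level pooling, and on positivity that rises with time. The absence of a visit term is silence in SAP 9.3, not a statement that visits are pooled. If the subject is the unit, as the Table 14.2.3.4 title suggests, and troughs are averaged over visits, the drift largely cancels and the repeated-sample problem goes. These points stand, but they also show that two places in the SAP disagree on the unit.

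The ANOVA is not the only look at ADA and exposure. SAP 9.1 plots individual concentrations over time by ADA group (Figure 14.2.3.7) and summarises concentrations by visit. SAP 9.2 derives model-based troughs separately for Weeks 4, 8, 12 and 16. A decline common to all subjects would be visible there.

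The bias may also be small beside the noise. Assume a trough CV of 40% to 60% (none is given) and 6 ADA+ against 54 ADA- samples, treated as independent. The standard error is CV × √(1/6 + 1/54), about 17% to 26%, so an 11% bias is roughly 0.4 to 0.6 of a standard error.

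Finally, a reader might infer that 16 weeks is too short. It is not: at 16.8 days the Week 16 trough is 101% of steady state. The 4-week sentence could also be meant loosely, but at 16.8 days only troughs from Week 8 on lie within about 12% of steady state.

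**Conclusion.** The conflict in Protocol 7.3.1 holds by arithmetic, given the protocol's one-compartment structure, linear kinetics and the 2:1 load. A 16.8-day half-life, implied rather than stated, puts the Week 4 trough about 37% above steady state, with a fall of about 26% by Week 16 (22% to 30% allowing for rounding). Steady state at Week 4 requires 28 days, and then 12 weeks is 3 half-lives. The documents do not show which figure is right. They therefore do not establish that the follow-up is too short, and the 16-week duration remains long enough at the 16.8-day half-life.

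The ADA consequence is conditional. A sample-level ANOVA could confound ADA status with visit. Under the assumed late-onset patterns the false deficit is about 6% to 14%; it is zero if positivity is constant over visits and reversed if it is early only. The unsettled unit of analysis and, for a sample-level analysis, the missing subject effect are defects at any half-life.

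**What to change.** In SAP 9.3 and Table 14.2.3.4:
- Settle whether the unit is the sample or the subject, and make text and title agree.
- Restrict the comparison to Weeks 4, 8 and 16, and state that Week 24 is not included as a trough.
- Include visit as a factor and subject as a random effect.

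In Protocol 7.3.1, reconcile the steady-state and half-life statements from the adult model's half-life and restate whichever figure does not hold. Apply the steady-state label to observed troughs only at visits that the reconciled half-life supports.

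The cost is a model statement, a table title and footnote, and a few protocol sentences, with no new data. The downside is lower precision for the ADA contrast. With few ADA+ samples the mixed model may be hard to fit.

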## 7.4 Selection of Study Population

### 7.4.1 Number of Planned Subjects

It is anticipated that approximately 30 subjects will be screened, with approximately 20 eligible subjects enrolled in approximately 10 study centers across the United States. Refer to the statistical considerations on which the numbers are based in Section 9.5.

[figure not shown]
#### 7.4.2 Inclusion Criteria

To be eligible for study entry subjects must satisfy all of the following criteria:

- Subjects ≥ 12 to < 17 years of age at the screening visit.

- Chronic AD for at least 2 years before the screening visit and confirmed according to the American Academy of Dermatology Consensus Criteria (Appendix 1) at the time of the screening visit.
- EASI score ≥ 16 at both screening and baseline visits.
- IGA score ≥ 3 (based on the IGA scale ranging from 0 to 4, in which 3 is moderate and 4 is severe) at both screening and baseline visits.
- AD involvement > 10% of Body Surface Area (BSA) at both screening and baseline visits.
- Peak (maximum) pruritus NRS score of at least 4.0 at both screening and baseline visits:

Docume response	ented recent history (within 6 months before the screening visit) of inade to topical medications (TCS with or without TCI).	quate

CONFIDENTIAL Page 41 of 99

- Agree to apply a moisturizer throughout the study from the screening visit daily, and liberally as needed; agree to apply an authorized TCS from the screening visit and throughout the study as determined appropriate by the investigator.
- 9. Women of childbearing potential must agree either to be strictly abstinent throughout the study and for 12 weeks after the last study drug injection or to use an effective and approved method of contraception throughout the study and for 12 weeks after the last study drug injection. This criterion also applies to a prepubertal female subject who begins menses during the study.

Effective and approved methods of contraception applicable for the subject and/or their partner are defined below:

- Progestogen-only oral hormonal contraception
- Male or female condom
- Cap, diaphragm or sponge with spermicide
- · Combination of male or female condom with cap, diaphragm or sponge with spermicide
- Combined (estrogen and progestogen containing-) oral, intravaginal, or transdermal hormonal contraception
- Injectable or implanted hormonal contraception
- Intrauterine devices
- Subject and guardian willing and able to comply with all of the time commitments and
  procedural requirements of the clinical trial protocol, including daily diary recordings by
  the subject using an electronic handheld device provided for this study.
- Understand and sign an Informed Consent Form (ICF) and Assent Form before any investigational procedures being performed.

CONFIDENTIAL Page 42 of 99

#### 7.4.3 Exclusion Criteria

Subjects will be excluded from the study if one or more of the following criterion are applicable:

- Body weight < 30 kg.

- Subjects meeting one or more of the following criteria at screening or baseline:
  - Had an asthma exacerbation requiring hospitalization in the preceding 12 months.
  - 2b. Reporting asthma that has been not well-controlled (ie, symptoms > 2 days per week, nighttime awakenings >1-3 times per week, or some interference with normal activities) during the preceding 3 months.
  - Asthma Control Test ≤ 19 (applies only for subjects with a history of asthma).
  - 2d. Peak expiratory flow < 80% of the predicted value.
- Subjects with a current medical history of chronic obstructive pulmonary disease (COPD) and/or chronic bronchitis.
- 4. Cutaneous infection within 1 week before the screening visit or any infection requiring treatment with oral or parenteral antibiotics, antivirals, antiparasitics, or antifungals within 1 week before the screening visit. Subjects may be rescreened once the infection has resolved.
- Requiring rescue therapy for AD during the run-in period, or expected to require rescue therapy within 2 weeks following the baseline visit.
- Positive serology results for hepatitis B surface antigen [HBsAg] or hepatitis B core antibody [HBcAb], hepatitis C antibody, or human immunodeficiency virus [HIV] antibody at the screening visit;

Note: Subjects with a positive HBcAb and a negative HBsAg can be included in this clinical trial if hepatitis B surface antibody (HBsAb) is positive (considered immune after a natural infection).

 Having received any of the following treatments in Table 5 within the specified timeframe before the baseline visit:

Table 5: Prior Treatments

Treatment(s):	Timeframe

CONFIDENTIAL Page 43 of 99

Treatment(s):	Timeframe

Note: These treatments should not be discontinued for reasons related to this clinical study.

- Subjects who failed to respond clinically to previous treatment with a biologic (eg, dupilumab) or a JAK inhibitor.
- Pregnant women (positive serum pregnancy test result at the screening visit or positive urine pregnancy test at the baseline visit), breastfeeding women, or women planning a pregnancy during the clinical trial.
- 10. History of lymphoproliferative disease or history of malignancy of any organ system within the last 5 years, except for (1) basal cell carcinoma, actinic keratoses or squamous cell carcinoma in situ (Bowen's disease) that have been treated and have no evidence of recurrence in the last 52 weeks before the baseline visit, or (2) carcinoma in situ of the cervix.
- History of hypersensitivity (including anaphylaxis) to an immunoglobulin product (plasmaderived or recombinant, eg, monoclonal antibody) or to any of the study drug excipients.
- History of intolerance to low or mid potency TCS or for whom TCS is not advisable (eg, hypersensitivity to TCS, significant skin atrophy, etc).
- 13. Known active or latent tuberculosis (TB) infection.
- Known or suspected immunosuppression or unusually frequent, recurrent, severe, or prolonged infections as per investigator judgment.
- History of or current confounding skin condition (eg, Netherton Syndrome, psoriasis, Cutaneous T-Cell Lymphoma [Mycosis Fungoides or Sezary Syndrome], contact dermatitis, chronic actinic dermatitis, dermatitis herpetiformis).
- 16. Any medical or psychological condition, or any clinically relevant laboratory abnormalities, such as but not limited to elevated ALT or AST (> 3 × ULN) in combination with elevated bilirubin (> 2 × ULN), at the screening visit that may put the subject at significant risk according to the investigator's judgment if he/she participates in the clinical trial, or may interfere with study assessments (eg, poor venous access or needle-phobia).

CONFIDENTIAL Page 44 of 99

- Planned or expected major surgical procedure during the clinical trial.
- Subjects unwilling to refrain from using prohibited medications during the clinical trial (see Section 7.5.8.2).
- 19. Currently participating in any other clinical trial of a drug or device, participated in a clinical trial within the past 3 months before the screening visit, or is in an exclusion period (if verifiable) from a previous clinical trial.

## 7.4.4 Removal of Subjects From Therapy or Assessments

Although the importance of completing the entire clinical trial will be explained to the subjects, any subject is free to discontinue his/her participation in the study at any time and for whatever reason, specified or unspecified, and without any prejudice. No constraints are to be imposed on the subject, and when appropriate, a subject may be treated with other conventional therapy when clinically indicated. Investigators or the sponsor can also withdraw subjects from the clinical trial if deemed to be necessary.

Subjects may stop study drug for any of the following reasons:

- Subject consent withdrawal
- · Use of non-permitted concurrent therapy
- Non-compliance with the study drug or study schedule
- Lost to follow-up
- Occurrence of AEs not compatible with the continuation of subject participation in the study, in the investigator's opinion, or unacceptable to the subject to continue
- Serious immediate-type allergic manifestations including anaphylactic reaction
- Pregnancy
- Use of systemic rescue therapy during the run-in period through the Week 12 visit (last study drug injection), unless otherwise specified in Table 8 of Section 7.5.8.2.
- Investigator request
- · Intercurrent illness
- Diagnosis of a malignancy (except curatively treated in situ cervical carcinoma or basal cell carcinoma)
- Any opportunistic infection (such as active TB and other infections whose nature or course suggest an immune-compromised status)
- Sponsor request
- Treatment failure

The reason(s) for withdrawal will be documented in the case report form (CRF). Subjects who have been enrolled and treated will not be replaced by another subject.

CONFIDENTIAL Page 45 of 99

Subjects who prematurely discontinue study drug will be encouraged to complete the scheduled study visits.

When a subject discontinues study drug, he/she will be fully assessed whenever possible. Subjects discontinuing study drug before the Week 16 visit should attend an early termination visit and a follow-up/final visit 12 weeks after the last study drug injection for safety follow-up.

Reasonable efforts will be made to contact subjects who are lost to follow-up. These efforts must be documented in the subject's file.

The sponsor has the right to terminate the study at any time in case of SAEs or if special circumstances concerning the investigational product or the company itself occur, making further treatment of subjects impossible. In this event, the investigator(s) will be informed of the reason for study termination.

